The enrollment log will track participant status from the pre-screen; approach status (e.g., consented, refused); self-report screen; randomization; and overall study status (e.g., active, completed, withdrawn, deceased). Some of this data may be automatically imported into REDCap from the Amalga query or entered directly into REDCap by a member of the study team. Follow-up assessment completion rates will also be tracked by condition in REDCap. This data will be checked against signed e-consent forms and patient-reported outcome data received.

The team is aware that at times, due to computer outage or lack of Wi-Fi access, the enrollment logging procedures may require the team to take alternative measures (e.g., computer/iPad or paper logging). If a study team member logs enrollment information or obtains written informed consent on a hard copy because

of technological issues, then the data is subsequently entered into the enrollment log in REDCap. In these instances, someone on the team other than the person who entered the data into REDCap will compare the accuracy of the entry into REDCap against the original data source (hard copy). Any hard copy data sources will be kept in locked file cabinets and any data with identifying information will be stored separately from de-identified study data.

2. Patient-Reported Outcomes

Patient-reported outcomes are collected using a variety of potential methods, such as REDCap, hard copy, emailed PDF and may be completed either by telephone, in person, or by the participant independently. Regardless of how they are collected, all patient-reported outcomes will ultimately be entered into REDCap, and then downloaded into computer software (e.g., SPSS, STATA) at the end of the study for data analysis. Data entered into REDCap from a hard copy will be checked by a second data enterer to ensure data entry accuracy from the hard copy version.

REDCap data quality will be monitored periodically by the study PI and/or data analyst. In the event that any changes need to be made to the data, these changes will be made directly in REDCap. There is a data logging tool in REDCap that allows administrators to track changes to the project. This tool provides access to an audit trail created by REDCap. For each entry that changes data in the database, REDCap records the date, time, username of the person logged in at that time, the type of event and the changes that were made. This audit trail in the data logging tool stores every entry/change throughout the life of the database. Specific checks for completion and accuracy are outlined below for the primary and secondary outcomes and for intervention and usual care activity. Certain patient-reported outcomes (PRO) will be used in the 'Anticipated AE/SAE' log as well. Specifically, PRO's on suicide and overdose will be reviewed as described above.

- Feasibility**

Feasibility measures include enrollment rates, retention rates at each outcome and followup assessment, intervention completion rates and number and types of contacts made by the interventionist. At team meetings, the CONSORT diagram will indicate enrollment and retention rates. At least monthly, the study RA/RC and PI will review the ED-LINC contact log in RedCap for completeness, accuracy and content. Feasibility of implementation will also be assessed using specific assessments of ED-LINC participants at the 6-month follow-up visit. The rates of completion of these assessments will be assessed.

- Substance Use and TLFB**

Past 30-day substance use will be obtained at baseline and every follow-up assessment and calendar will be used to track substance use on specific days. Prior to performing this assessment, members of the study team will receive training on TLFB methods including a webinar published by NIDA, review of the methods with current NIDA CTN project coordinators that have performed these assessments for a variety of substances in a variety of settings including the ED and will practice obtaining this data with practice participant encounters. This training will be completed prior to study start to ensure accuracy of obtaining this data. Episodic shadowing by study PI will be done to ensure there isn't drift of accuracy in data collection. TLFB data will be captured on a hard copy calendar and transferred to RedCap by study staff. The hard copy will not contain any PHI and be labeled with a study ID and will be kept in a locked cabinet in a locked

office. At least 25% of these forms will be double-entered into RedCap to ensure accuracy of data entry.

- **Health Care Utilization**

Emergency department (ED) utilization will be assessed throughout the duration of the trial using either the UW EMR system (e.g., the UW Amalga data repository) or the Emergency Department Information Exchange (EDIE) web-based platform on an approximately monthly basis. Additionally, EDIE data will be pulled for all consented patients to capture all ED visits, inpatient visits and any available outpatient visits from five years before enrollment up to five years after enrollment in the trial.

- **ED-LINC Intervention and Usual Care**

The study team will document ED-LINC intervention activities in REDCap. These notes are not static and are modifiable over the course of the trial. For instance, information may be added or modified as a consequence of supervision discussion. The study team will review documentation during team meetings and case conference supervisions and update notes as needed to provide the most complete and accurate picture of what transpired. The data logging tool in REDCap allows administrators to track these types of historical changes. REDCap records the date, time, username of the person logged in at that time, the type of event and the changes that were made. This audit trail in the data logging tool stores every entry/change throughout the life of the database which will help the study team check completeness of intervention data.

The study team will document how many and what type of consults each patient in the usual care (UC) condition receives. This consultation information will be obtained primarily from the EMR and entered in to REDCap. The team will rely on information from the EMR to ensure completeness and accuracy of all UC documented in REDCap

VIII. INTERIM ANALYSIS PLANS

Interim analysis is not relevant as this is a pilot study and effect sizes are not being measured.

IX. CONTENT AND FREQUENCY OF DSM REPORTS TO NIDA

Annually, the PI ([name]) will submit a grant report (RPPR) to NIDA. The grant report is due in June every year and will include details on:

- Study progress which will include details on feasibility measures, secondary outcomes including substance use and health care utilization and any problems reported to the IRB. An enrollment table will be completed per NIH guidelines
- Responsible conduct of research training received

References

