further for eligibility using the participant eligibility summary (PES). Eligible participants will undergo informed consent procedures and a total of 60 participants will be randomized to the collaborative care intervention (n = 30) or care as usual (n =30) condition. Intervention activity will continue for three months after the ED visit, while follow-up continues for six months after the ED visit. Primary outcomes include feasibility. Secondary outcomes include substance use measured by days of use of opioids as well as utilization of healthcare services including ED visits, primary care visits, mental health visits and substance use treatment visits.

1. Aims and Hypotheses

- 1) The primary aim** of the investigation is to determine the feasibility of the collaborative care intervention initiated from the ED and delivered longitudinally. Taken together, all elements of the intervention are referred to as ED-LINC. Feasibility measures include enrollment rates, retention rates at each outcome and follow-up assessment, intervention completion rates and number and types of contacts made by the interventionist. Feasibility of implementation will also be assessed. Guided by Proctor's taxonomy of implementation outcomes⁷, acceptability, feasibility and fidelity to ED-LINC will be measured.
- 2) The secondary aims** of the study are to determine differences in substance use and health care utilization between the two arms. While the study is not powered to detect a difference as this is a feasibility pilot study, substance use and health care utilization will be measured. Specifically, substance use will be measured utilizing a time-line follow back calendar administered by the research assistant to determine days of heroin or illicit opioid use and days of prescription opioid misuse. Additionally, EDIE will be utilized to determine ED utilization and inpatient admissions across Washington, Oregon, Alaska and other areas that EDIE is active. Participants will provide self-report information on primary care visits, mental health and substance use treatment visits. Engagement in substance use treatment will be confirmed via phone by study staff at all periods of assessment.

2. Participants

a. Inclusion Criteria:

- Aged 18-65
- Patients with at least one risk factor for opioid use disorder via the EMR pre-screen

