The study team member will provide an overview of the study and provide an unsigned copy of the informed consent to the potential participant, allowing ample time to read. If the patient is interested in participating, the study team member will review the informed consent verbally with the participant, answer any questions and obtain a signature on the consent form located in RedCap. If a patient does not want to consent to the study, the study team member will politely inquire rationale behind the refusal and this will be tracked as part of the main outcome related to feasibility. In previous studies, reasons for refusal at this point have included 'too much pain', 'not interested', 'do not want to do follow-up surveys and/or other study procedures' and 'discharged and don't want to wait'.

D. Randomization

After participants have undergone informed consent, the randomization procedure will take place. The investigation will employ a blocked randomization strategy with random assignment of block size of either 4 or 6 participants. Randomization will also be stratified by inclusion for prescription opioid misuse based on a NIDA m-ASSIST score of ≥ 4 for prescription opioid misuse. It is hypothesized that the majority of participants will screen in for illicit opioid use and stratified randomization will be used to ensure balance of participants with prescription opioid misuse given this is an important but likely small population of participants. Participants will be randomized to the following conditions:

- a. Usual Care control condition
- b. ED-LINC 2.0

Study condition will be assigned using the RedCap randomization module which will be programmed prior to study start by a data analyst. After the study team member obtains informed consent, randomization of condition will be performed using RedCap and the participant will be notified of their random assignment.

E. Baseline Interview

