I. STUDY IDENTIFICATION INFORMATION

TITLE OF PROTOCOL: Emergency Department Longitudinal Integrated Care 2.0 (ED-LINC 2.0)

PRINCIPAL INVESTIGATOR: [name] MD MS

FUNDER OF PROTOCOL: National Institute of Drug Abuse (NIDA)

CLINICALTRIALS.GOV: A description of this clinical trial will be available on <http://www.clinicaltrials.gov>, as required by U.S. Law. **NCT03699085**

SAP Version date: September 2021

Table of Contents:

Summary of Clinical Trial Features.....	Page 3
Primary Outcome Measures.....	Page 4
Refusal Rates	
Follow-up Completion Rates	
ED-LINC Intervention and usual Care process Outcomes	
Implementation Appropriateness	
Satisfaction	
Perception of Care Coordination	
Secondary Outcome Measures.....	Page 5
Substance Use	

Summary of Clinical Trial Features:

The *Emergency Department Longitudinal Integrated Care* (ED-LINC) intervention is a stepped collaborative care model of care initiated from the ED for patients with OUD that combines evidence-based treatment elements, proactive care coordination and population-level outcome tracking. ED-LINC builds upon previous work by tailoring the collaborative care model for patients at high risk for OUD presenting to the ED. A central objective of ED-LINC is to provide evidence-based treatment for OUD and related co-morbidity while in the ED in conjunction with proactive longitudinal care coordination that links patients to ongoing treatment. Weekly caseload supervision with measurement-based care outcome tracking allows for the stepping up of care for patients with recalcitrant symptoms, as well as opportunities to oversee care management linkages to community services targeting the key outcomes of initiation of MOUD and retention in MOUD treatment.

The main objective of this study was to conduct a pilot pragmatic randomized clinical trial of ED-LINC (n=20) compared to usual care (n=20) for ED patients at a single-site at high risk for OUD. The primary outcomes of this study pertain to feasibility of the model, research strategy and implementation.

Primary Outcome Measures

All primary outcome measures used **descriptive statistics**

Refusal Rate was calculated as the number of patients that refused or declined the self-report screening procedure in the ED divided by the eligible number of patients that could have done the self-report screening during the enrollment period.

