Follow-up Completion Rates were calculated for each followup timepoint and were calculated as the number of participants that completed follow-up divided by the total number of participants randomized to each arm of the trial. The 6-month followup completion rate is shown as the number of participants that completed the 6-month self-report interview divided by the number of participants randomized to each arm.

ED-LINC Intervention and usual Care process Outcomes were determined from extensive research notes. Specifically the EDLINC interventionist conducted a process validity assessment and documented the number of unique ED-LINC elements completed for each participant in the intervention.

Implementation Appropriateness was calculated by providing this validated self-report measure to each participant randomized to the ED-LINC assessment. Results were dichotomized to calculate the frequency of participants who 'agreed' or 'completely agreed' that the intervention was 'applicable' and 'seemed like a good match' to document appropriateness.

Satisfaction was calculated using a validated satisfaction questionnaire and provided to all participants at six-months. Each participant will complete the questionnaire and their results will be summed. The median and IQR range will be calculated for participants in each group that complete the assessment.

Perception of Care Coordination will be done using questions from a validated scale. The Wilcoxon Rank Sum test will be used to determine if there are significant differences between groups.

Secondary Outcome Measures

Substance Use

Substance use will be measured using the timeline follow back procedure which is a validated calendar method to determine days of use in a certain calendar period. First, we will sum days of use of illicit opioid use in 30 days at baseline and each followup period for each participant. The mean days of use/30 days with an associated standard deviation will be calculated at each time-period for both the ED-LINC intervention and the usual care control groups.

Next, we will evaluate variance of the data and test model fit on unadjusted data using different distributions. Given previous work, we anticipate the data to be skewed and zero-inflated. Thus, we hypothesize that we may use a normal Gaussian, Poisson or negative binomial distribution.

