Once model fit is determined, a reverse stepwise selection will be performed using a linear regression of clinician-selected input variables, alongside the intervention and TLFB timepoint, and an elimination threshold of $p > 0.05$

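### The SAP's illicit-opioid-days model does not require the randomisation stratum (prescription-misuse m-ASSIST of 4 or more) to be offered or kept; it should be a fixed term in a model that handles repeated measures

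*Protocol*

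**What the plan says.** Protocol III.D uses a "blocked randomization strategy with random assignment of block size of either 4 or 6 participants" and adds a stratification factor: "Randomization will also be stratified by inclusion for prescription opioid misuse based on a NIDA m-ASSIST score" of 4 or more. Its stated purpose is balance: "stratified randomization will be used to ensure balance of participants with prescription opioid misuse given this is an important but likely small population of participants".

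The SAP does not mention the factor. Under Secondary Outcome Measures, Substance Use, the outcome is built from illicit use alone: "First, we will sum days of use of illicit opioid use in 30 days at baseline and each followup period". After a distribution has been chosen on fit (Gaussian, Poisson or negative binomial), backward selection is run on "clinician-selected input variables, alongside the intervention and TLFB timepoint", with removal at p > 0.05. The candidate variables are not listed, no term is declared exempt from removal, and no term or correlation structure is named for several timepoints from the same person.

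The documents give two sample sizes. Protocol II.B has "a total of 60 participants will be randomized to the collaborative care intervention (n = 30) or care as usual (n =30) condition", and the SAP summary has "ED-LINC (n=20) compared to usual care (n=20").

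**The concern.** The stratum was chosen in the design, so the analysis would normally carry it. Here it may also predict the outcome. The Protocol separates prescription misuse from a majority expected to qualify on illicit opioids, while the SAP outcome counts only illicit-opioid days. Someone who qualified on the prescription score alone would be expected to report few such days.

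Stratified allocation removes most of the between-stratum variation from the arm difference. A model without the stratum leaves that variation in the residual, so at a single timepoint its standard error exceeds the real sampling error and the test is conservative. Leaving the choice to an unlisted candidate set and a p-value rule also means that a design factor is in or out of the model depending on the data.

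**Working it through.** **The plan's own figures.** There is no power or precision calculation to reproduce. The arms sum as stated (30 + 30 = 60 in the Protocol, 20 + 20 = 40 in the SAP). The check uses 40, the SAP's figure; width ratios at 60 were nearly the same.

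**Inputs.** From the documents: two strata, blocks of 4 or 6, equal arms, and about 20% attrition (Protocol, Follow-up Interviews). Assumed, because neither document gives them: stratum share p, the gap d between strata in within-stratum SDs, and the within-person correlation ρ. With an assumed SD of 10 days, d = 0.5, 1 and 1.5 are gaps of 5, 10 and 15 days.

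**Step 1: one timepoint, stratum left out.** The ratio of the SE without the stratum to the SE with it is √(1 + p(1 − p)d²).

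| d | p = 0.15 | p = 0.35 |
|---|---|---|
| 0.5 | √(1 + 0.1275 × 0.25) = 1.016 | √(1 + 0.2275 × 0.25) = 1.028 |
| 1 | √1.1275 = 1.062 | √1.2275 = 1.108 |
| 1.5 | √(1 + 0.1275 × 2.25) = 1.134 | √(1 + 0.2275 × 2.25) = 1.230 |

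Simulation with stratified blocks of 4 or 6 and n = 40 agrees: 1-3%, 6-11%, and up to about 24% at the last corner. Most of this is an overstated SE rather than a noisier estimate. In a separate simulation with 20% dropout and shares of 10-30%, the true SD of the estimate rose by only 2-3% at d = 1.

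**Step 2: the stratum is mixed.** It contains everyone with a prescription score of 4 or more, including people who also use illicit opioids. Suppose half of them (assumed) resemble the other stratum. The mean gap halves and the within-stratum variance rises, so the ratio becomes √(1 + 0.25p(1 − p)d² / (1 + 0.25pd²)).

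- d = 1, p = 0.15: √(1 + 0.0319/1.0375) = 1.015
- d = 1.5, p = 0.35: √(1 + 0.1280/1.1969) = 1.052

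The overstatement is then about 2-5%.

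**Step 3: the stratum is offered to backward elimination.** With n = 40, 20% dropout, shares of 10-30% and gaps of 0 to 2 SD, interval width relative to forcing the stratum in was 0.99 to 1.00, with coverage of 94.5% to 96.0%. The stratum was kept in 37-68% of runs at d = 1 and 84-99% at d = 2.

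**Step 4: the stratum is kept but does not predict the outcome.** At d = 0 the width without it divided by the width with it was 0.991 to 0.995, so keeping it costs about 1% or less.

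**Step 5: repeated timepoints.** If m rows per person are pooled in an ordinary regression, the true SE of a between-person effect divided by the naive SE is √(1 + (m − 1)ρ).

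- m = 3: √1.6 = 1.26 at ρ = 0.3; √2.4 = 1.55 at ρ = 0.7
- m = 4: √1.9 = 1.38 at ρ = 0.3; √3.1 = 1.76 at ρ = 0.7

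In simulation with three pooled timepoints and the stratum omitted, type I error was about 6-19%. Adding the stratum without a participant term raised it to about 12-23%, because the conservative error no longer offset part of the anti-conservative one.

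**The case against.** The strongest reply is that the stratum may well be among the clinicians' variables, and that Step 3 shows almost nothing is lost once it is offered. This stands. A loss at a single timepoint requires the stratum to be left off the list and also to be clearly prognostic. What remains is that the SAP does not require it to be offered.

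A reader might infer that intervals for illicit-opioid days will be too wide, and tests conservative. The documents do not support this as a general statement. Step 5 shows that pooled timepoints without a participant term push the other way and can dominate, and a Poisson fit to overdispersed counts would do the same.

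A reader might also infer that the design bought precision that the analysis then discards. Protocol III.D claims balance, not precision, and Protocol II.B.1 says that the pilot is not powered for arm differences. No loss of power can be quoted, because neither document gives an effect size or an SD.

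Finally, a reader might want the rank test stratified too, since the SAP says: "The Wilcoxon Rank Sum test will be used to determine if there are significant differences between groups". That test is on perception of care coordination, not opioid days, and nothing in the documents suggests that the stratum predicts it.

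**Conclusion.** The gap in the SAP is real and small. Randomisation is stratified, and the illicit-opioid-days model neither requires the stratum as a candidate nor protects it from removal. At one timepoint with 40 participants, leaving it out would overstate the SE by 1-3% at a half-SD gap, 6-11% at 1 SD, and up to about 24% at 1.5 SD with a 35% share. That last corner sits poorly with a subgroup that the Protocol expects to be small. If half the stratum also uses illicit opioids, the 1 to 1.5 SD gaps give about 2-5%. All these figures rest on assumed shares, SD and gaps. For the SAP as written, the net direction of the error cannot be determined. This is a point to consider, not a serious flaw: the outcome is secondary, and the trial is a feasibility pilot.

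**What to change.** In the SAP's Substance Use section, state that the randomisation stratum (prescription-misuse m-ASSIST of 4 or more) enters the illicit-opioid-days model as a fixed term exempt from stepwise elimination, or say why not. Optionally add the illicit-opioid m-ASSIST of 4 or more, already collected at screening, as a second fixed indicator. It separates prescription-only participants from those positive on both scores.

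In the same sentence, specify how repeated timepoints are handled, for example a participant random effect or generalised estimating equations with robust standard errors, under whichever distribution is chosen. The two changes belong together: Step 5 shows that adding the stratum alone could raise the type I error.

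The cost is a sentence or two in the SAP and one or two degrees of freedom for the fixed terms. No new data are needed. If the stratum turns out not to predict the outcome, the interval widens by about 1% or less. The rank test can stay as it is.
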